Sample size calculations were performed using the formula adapted by Lindsey to take advantage of the power gained from obtaining repeated measurements across time and eyes (Lindsey, 2001). Data from the Berkeley Infant Biometry Study (BIBS) were used to obtain an estimate of the within-subject/within-visit repeatability of refractive error and the correlation of these measurements across time. The standard deviation for change in refractive error from 3 to 9 months of age from infants with hyperopia $>+5.00\text{D}$ enrolled in BIBS was 1.17D. Data from Atkinson et al. suggests a standard deviation of 1.50D and Ingram et al. give a standard deviation for change is assumed to be 1.36D (Atkinson et al., 2000; Ingram et al., 2000). To provide the most conservative estimate of sample size, the standard deviation of change is assumed to be 1.50D. If a new, difficult, expensive treatment strategy is to be adopted, the benefit must be substantial. The ordinary decrease in hyperopia in uncorrected, highly hyperopic infants might be 1.2D to 1.34D (Atkinson et al., 2000; Ingram et al., 2000). We would expect that there would be little enthusiasm for this new approach if the decrease in hyperopia in treated infants was not on the order of 3.00D (an improvement compared to controls of 1.75D). Using these parameters, a sample size of 13 in each randomized group will be needed ($\alpha=0.05$, $\beta=0.1$, two-sided test). If we estimate that 10% of the infants may not complete the follow up, 30 infants need to be enrolled with 15 randomly assigned to each of the two randomized groups. The rather large difference relative to its standard deviation to be detected ($1.75/1.50 = 1.17$) along with the increase in power obtained by taking repeated refractive error measurements help to keep the sample size low. However, given the prevalence of high hyperopia (more than $+5.00\text{D}$) in the population of 3 months old infants, a sample size of 30 eligible infants (for randomization, not including the case series) is not trivial. Up to 10 eligible infants will be enrolled in the case series portion of the study. One of the major efforts in this project will be screening the 900 infants needed to find those that are eligible.

C. Measurement/Instrumentation

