There is no universally accepted outcome measure for infant accommodative response, therefore the analysis in this phase will be somewhat exploratory. The simplest metric to calculate would be the average accommodative response. However, variability in that response provides a useful perspective that distinguishes the infant with stable accommodation from the one that is less well-controlled or exhibits more of a searching accommodative behavior. Variability will be added as a covariate in analyses of the accommodative response. The simple standard deviation in accommodation is one measure of this variability. Another approach would be to look for periodic variability through Fourier analysis of the response. This analysis would be exploratory. Analyses are typically of 10 second segments of response. If infants are too unsteady to give such lengths of uninterrupted data, then the analysis may not be feasible. If the analysis can be done, then power at low, mid, and high temporal frequencies will be used as covariates in the analyses of accommodative response. Other potential metrics might be lag-minutes or diopter-minutes, essentially area-under-the-curve summary measures of diopters of lag, or alternatively, diopters of accommodative response per minute of recording.

- vi. **Cycloplegic refractive error** will be measured at all visits. Refractive error will be measured by **cycloplegic retinoscopy** by a masked examiner (primary outcome of the treatment phase of the study). The parents of the subject will be instructed not to discuss the treatment group the patient is in to the masked examiner. Measurements will occur 30 minutes after drop instillation. One drop of proparacaine 0.5% will be instilled in each eye, followed by two drops of cycloplegic agents. The drops used for cycloplegia are the following:
 - 1. Tropicamide (1%) will be used only at the screening visit
 - 2. Cyclopentolate (1%) will be used during all remaining visitsThe neutral point for the horizontal meridian is recorded first, then the neutral point for the vertical meridian. If the axes are oblique, the true meridian is measured by projecting the retinoscopy beam on to a protractor on the wall. **SureSight autorefraction** will be also be performed on both eyes from 35cm by the investigator (unmasked).

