f. **Development of Strabismus.** The subject population of this study is at risk for developing strabismus (Anker et al., 2004; Cotter, 2007; Pascual et al., 2014). This will be discussed with the parents of potential subjects during screenings and during the consent process prior to the baseline examination. If a subject develops a strabismus, the subject will be discontinued from treatment in the study. The subject cannot remain in either arm of the study because of the different standard of care in prescribing philosophy that occurs with the development of strabismus (typically providing a full refractive correction for hyperopia). The subject will remain in the study and will continue to be followed for observation of all study measurements and outcomes. The subject's parents will have the option of their child remaining under the care of [name] in the Ohio State University College of Optometry Pediatric clinic, or any other doctor within the Ohio State University College of Optometry, or seek or be referred to another provider for a second opinion or for patient care. Any visits or treatment of strabismus or any clinical sequelae of the strabismus would be at the discretion of the licensed eye care provider and separate from the study. Follow up visits related to the study will follow the same schedule and contain the same measurements listed in the protocol.

E. **Internal Validity.** There are no threats to internal validity. All procedures performed in the examination are standard procedures that have been performed frequently in other studies. Threats to external validity might be present in selection bias. The sample of patients to be recruited will be identified at Riverside Pediatrics Associates by screenings of age appropriate infants. The screenings will be performed by [name], [name], or a nurse that has been adequately trained. The age, gender, and ethnicity of these patients might not be a true representation of the general population of full term, healthy infants.

F. **Data Analysis.** All data analysis will be performed using SPSS (Version 24). Statistical significance will be assessed using two-sided tests with an alpha level of 0.05. Data from both eyes will be included in all analyses and techniques to control for intra-subject correlations will be used.

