The basic analysis will be a two-sample t-test comparison of the change in refractive error between the two groups at 9 months and again at 18 months of age. Analysis of Covariance (ANCOVA) will be used to compare the change in refractive error between the two treatment groups adjusting for any possible confounding variables. Refractive error at 3 months along with any other identified confounders will be included as covariates in the analysis. Randomization of infants into the two treatment groups should protect against confounding, however, testing will be performed and adjustments made for imbalances in confounders between groups.

The relationship of accommodative effort and accommodative lag with change in refractive error between 3 and 9, or 3 and 18 months will be analyzed by repeated measures analysis of variance. We will fit a linear functions describing the relationship between change in refractive error and accommodation as the repeated factor, either effort or lag. A significant effect for type of accommodation will indicate that the greater slope is the better explanation of the driving force for change in refractive error.

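### The arm comparisons at 9 and 18 months use only infants measured at that age, so loss that follows earlier progress differently in the two arms would bias the effect, although earlier masked readings are on file

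*Combined protocol and SAP*

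**What the plan says.** Section F (Data Analysis) gives two methods for the treatment effect on refraction. The first is a "two-sample t-test comparison of the change in refractive error between the two groups at 9 months and again at 18 months of age". The second is an ANCOVA of change, adjusted for the 3-month value and any identified confounders. Repeated-measures analysis of variance is named only for relating accommodation to refractive change, not for comparing the arms. The text available for review has no missing-data rule, analysis population or sensitivity analysis for the arm comparison.

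The sample size paragraph, just before section C, allows for loss: "If we estimate that 10% of the infants may not complete the follow up", then "30 infants need to be enrolled with 15 randomly assigned to each of the two randomized groups". Section D.e counts a visit outside its window as missed.

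Section D.c.vi has cycloplegic retinoscopy done "by a masked examiner (primary outcome of the treatment phase of the study". The table in section D.d marks it as masked at 4.5, 6, 9, 12, 15 and 18 months of age.

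**The concern.** An infant lost after the 15-month visit has five masked outcome readings after baseline, and the 18-month test uses none of them. The same holds for an infant examined one day late: the V7 window closes at day 464, so an examination on day 465 counts as missed. Adjusting for the 3-month value does not help, because it says nothing about progress since then.

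Parents know whether their infant wears spectacles, so the reasons for leaving could differ between arms. Parents of a control infant who is progressing slowly might seek care elsewhere. Parents of a treated infant already out of spectacles might see less reason to return. With 15 infants per arm, two absences can move an arm mean. The sample size paragraph also claims power from repeated measurements across time, yet each stated arm comparison uses only baseline and one later visit.

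**Working it through.** **Inputs from the sample size paragraph.** Control decrease about 1.25D, treated 3.00D, difference 1.75D, SD of change 1.50D, 15 enrolled and 13 needed per arm, 10% loss. **Assumed, because the documents do not give it:** correlation ρ of 0.6 to 0.9 between change at 15 months and change at 18 months.

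**The plan's own figures.** The dropout step reproduces: 13 / 0.90 = 14.4, so 15 per arm and 30 in all. The 13 cannot be checked. The ordinary two-mean formula gives 2 × [(1.960 + 1.282) × 1.50 / 1.75]² = 15.4, so 16. The plan instead uses a repeated-measures formula whose correlation and number of measurements are not stated. With the factor (1 + (m − 1)ρ)/m, where ρ is the correlation between repeated readings, 13 follows for ρ of about 0.55 to 0.68 with m = 2, or 0.73 to 0.81 with m = 6. It is therefore attainable.

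**Size of the bias, simple identity.** Shift in an arm mean = fraction lost × gap between lost and retained infants. With 2 of 15 lost and an assumed gap of 0.75 to 1.50D (0.5 to 1 SD):

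- one arm: 2/15 × 0.75 = 0.10D to 2/15 × 1.50 = 0.20D
- both arms, opposite directions: 0.20 to 0.40D

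**Near-worst case.** Suppose exactly the two least-improved controls at 15 months leave. The two most extreme of 15 standard normal values average (1.736 + 1.248)/2 = 1.492 in absolute size. The mean of the 13 who stay shifts by 2 × 1.492 / 13 = 0.230 SD, which is 0.230 × 1.50 × ρ = 0.344ρ dioptres at 18 months.

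| ρ | Selective loss in one arm | Opposite loss in both arms |
|---|---|---|
| 0.6 | 0.21D | 0.41D |
| 0.8 | 0.28D | 0.55D |
| 0.9 | 0.31D | 0.62D |

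Simulation agrees: 0.21 to 0.32D in one arm and 0.42 to 0.63D in both. Losing the two most-improved treated infants gives the same size. Both patterns shrink the effect. Loss of slow responders from the treated arm would inflate it.

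**Softer loss.** If the chance of leaving rises gradually with poor progress, in controls only (assumed log-odds slope 0.5 to 1 per SD), the bias is 0.07 to 0.17D. At a slope of 1.5, with slow responders leaving the treated arm only, it is 0.12 to 0.22D for ρ of 0.5 to 0.9.

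**No bias.** If loss is random, or the two least-improved infants leave in both arms, the completer difference is within about 0.01D of the truth.

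**What the earlier readings recover.** A likelihood estimate using the 15-month reading is within about 0.02D of the truth whenever loss depends on that reading. Under random loss its standard error is about 2% to 5% smaller. If loss instead follows the unseen 18-month value (lowest two controls), the likelihood estimate is still off by 0.24D at ρ = 0.6, against 0.34D for completers, and by about 0.08D at ρ = 0.9.

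The 9-month comparison was not simulated. Only the 4.5- and 6-month follow-up readings precede it.

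**The case against.** The plan takes real steps against informative loss. Treated infants who come out of spectacles are followed to 18 months (section D.b.ii), which bears directly on the early-success route. Poor spectacle wear is not a reason for discontinuation (D.b.ii). Infants who develop strabismus stay in follow-up with all measurements (D.f). The windows for the two analysed visits, V4 and V7, are extended (D.e). The slow-progress route in controls is conjecture, and the plan itself regards uncorrected infant hyperopia as symptom-free (D.b.iii). All of this stands. It lowers the risk, but it does not prevent withdrawal or a late visit.

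The size also needs context. Losing exactly the two most extreme infants is close to the worst that two losses can do, and four of 30 is 13%, against the planned 10% (three infants). The completer standard error is about 1.50 × √(2/13) = 0.59D, so the one-arm near-worst case is roughly half a standard error.

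Section F's promise to control for within-subject correlation could be met by a mixed model. However, the sentence concerns using both eyes and does not bring the interim visits into the arm comparison.

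A reader might infer that any loss related to progress biases the result. It does not: the dependence must differ between arms. A reader might also infer that a repeated-measures model removes the problem. That holds only if loss depends on recorded readings. Nor do these figures show that 13 per group is wrong, since the inputs to its formula are not given.

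**Conclusion.** The point holds in conditional form. That the comparisons rest on infants seen at the given age follows from the methods named and the absence of any missing-data rule; the plan does not say so outright. Bias in the arm difference requires loss that tracks earlier progress differently in the two arms. Under that condition, with two of 15 lost per arm and ρ of 0.6 to 0.9:

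- near-worst case, one arm: about 0.2 to 0.3D, or 11% to 17% of 1.75D
- near-worst case, opposite directions: about 0.4 to 0.6D, or 23% to 34%
- probabilistic loss, one arm: about 0.1 to 0.2D

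Otherwise the bias is about zero and the cost is a small loss of precision. The documents do not show that such loss will occur. The change is worth making because the readings are already scheduled and the remedy is cheap. It would also bring the analysis closer to the repeated-measures basis claimed for the sample size.

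**What to change.** In section F, make the main arm comparison a likelihood-based repeated-measures model of masked cycloplegic retinoscopy at all follow-up visits. Use the mean of the two eyes per infant, or eye nested within infant. Include arm, visit, arm-by-visit and 3-month refraction, with a simple covariance structure fixed in advance and a small-sample degrees-of-freedom correction. Read the arm differences at 9 and 18 months from this model.

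State that it assumes loss depends only on recorded readings. Keep the single-age t-test and ANCOVA as sensitivity analyses. Add one that shifts the values assumed for missing infants separately by arm, because the completer tests do not probe that assumption.

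The cost is analysis wording and modest programming, with no new visits, data or infants. The main drawback is that a covariance structure must be chosen in advance for about 30 infants. With complete data the estimates are essentially those of the single-age ANCOVA, and under random loss the precision gain is only about 2% to 5%.

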- vii. **Peripheral refractive error.** Peripheral refractive error will be assessed by the examiner using the SureSight autorefractor as an estimate of the ocular shape during emmetropization. The subject's gaze is directed towards toys or interesting targets. Measurements will be made at 30° in both left and right gaze (a total of 2 peripheral gazes). This will be measured at the baseline, 9 month, and 18 month visit.
- viii. **Parental refractive error status.** The parent(s) refractive error will be obtained as in the Berkeley Infant Biometry Study (BIBS), from the prescription for glasses provided by the eye care provider for parents who wear refractive correction. If the parents report not having had a recent eye

examination, refractive error status will be estimated with the autorefractor without cycloplegia.

ix. Survey. Additional data will be collected via a survey administered at the baseline visit and will request information regarding:

1. Parental age at the infant's birth
2. Parental smoking status
3. Alcohol consumption
4. Infant birthweight
5. Birth order
6. Minor complications of pregnancy and delivery
7. Years of education completed for each parent
8. Family income
9. Ethnic identification for each parent and for the child (assigned by the parent)

x. Additional data. The following data will be obtained at each visit:

1. Significant infant illness
2. Medications given to the infant
3. Nutritional history
4. Compliance with spectacle wear. Parents will fill out a form at each follow up visit listing how compliant the subject was wearing spectacles. Parents of the subjects will be able to classify compliance as very good ($\geq 75\%$ of the time), good ($\geq 50\%$ of the time but less than 75% of the time), fair ($\geq 25\%$ of the time but less than 50% of the time), or poor ($\leq 25\%$ of the time). Parents will be given a pre-printed calendar to help them keep track of compliance on a daily basis. This will be turned into the investigator at the next follow up.

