Relative peripheral refractive error will be calculated as the difference in peripheral and central cycloplegic refractive error. This relative peripheral refractive error calculation will give insight into the ocular shape of the subject. If the relative peripheral refractive error is relatively myopic compared to the central refractive error, the eye has a more oblate shape. If the relative peripheral refractive error is relatively hyperopic compared to the central refractive error, the eye has a less oblate or more prolate shape. The relationship of the change in peripheral refractive error and central refractive error (relative peripheral refractive error) will be analyzed by a two-sample t-test comparison of the change in the relative peripheral refractive error between the two groups at 9 months and again at 18 months of age. Analysis of Covariance will be used to compare the change in relative peripheral refractive error between the two treatment groups adjusting for any other possible confounding factors. Peripheral refractive error at 3 months along with any other identified confounders will be included as covariates in the analysis. Randomization of infants into the two treatment groups should protect against confounding, however, testing will be performed and adjustments made for imbalances in confounders between groups.

IV. Bibliography

Blade, P.J. & Candy, T.R. (2006). Validation of the PowerRefractor for measuring human infant refraction. *Optom Vis Sci*, 83, 346-53.

Cook, R.C. & Glasscock, R.E. (1951). Refractive and ocular findings in the newborn. *Am J Ophthalmol*, 34, 1407-13.

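### Beyond the 3-month value, the ANCOVA covariates are left open and chosen by testing the randomised arms for imbalance, so the adjusted estimate depends on chance and loses precision

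*Combined protocol and SAP*

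**What the plan says.** Section F (Data Analysis) plans two comparisons of change in refractive error. The first is unadjusted: "The basic analysis will be a two-sample t-test comparison of the change in refractive error between the two groups at 9 months", repeated at 18 months. The second is an ANCOVA "adjusting for any possible confounding variables". One covariate is fixed and the others are open: "Refractive error at 3 months along with any other identified confounders will be included as covariates in the analysis". The paragraph notes that randomisation should guard against confounding, and then says that "testing will be performed and adjustments made for imbalances in confounders between groups".

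The paragraph on relative peripheral refraction repeats the rule: "Peripheral refractive error at 3 months along with any other identified confounders will be included as covariates in the analysis".

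No candidate list, significance threshold or maximum number of covariates is given. Nothing says that covariates must be measured before randomisation. Section D.c.vi names retinoscopy "by a masked examiner (primary outcome of the treatment phase of the study" as the outcome, but neither the t-test nor the ANCOVA is named as the primary analysis.

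**The concern.** If allocation is sound, any baseline difference between the arms is chance. A test for imbalance then carries no information on whether a variable predicts refractive change. It selects variables for their correlation with arm, which is the property that inflates the standard error of the treatment effect. A prognostic variable that happens to be balanced is left out, although including it would add precision.

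The pool could be wide. Under Survey (D.c.ix), "Additional data will be collected via a survey administered at the baseline visit" on nine listed items, several of them recorded for each parent, and parental refraction is collected as well. The content of the adjusted model is unknown until the arms have been compared, and two analysts following the text could report different adjusted results from the same data. The trial plans to analyse 13 infants per arm after screening 900, so it has little information to spend on noise covariates.

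**Working it through.** **Inputs from the sample size paragraph (before section C) and section F.** Difference 1.75 D, SD of change 1.50 D, two-sided alpha 0.05, beta 0.1, 13 analysed per arm, 10% loss.

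**The plan's own figure.** The plain normal formula gives n = 2 × (1.960 + 1.282)² × 1.50² / 1.75² = 15.4, so 16 per arm. The plan's 13 uses a repeated-measures gain. With two eyes, 15.4 × (1 + ρ)/2 = 13 at a between-eye correlation ρ of about 0.68. That correlation is not stated, so 13 can be neither confirmed nor refuted. 13/0.9 = 14.4 gives 15 per arm and 30 in total, as stated. With one value per infant, a t-test at 13 per arm has 81% power.

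**Assumptions, because the plan gives none.** 5 to 15 independent candidates, flagged at p < 0.05; one value per infant. Using both eyes would raise absolute power, but the number of randomised units stays at 26.

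**Chance of at least one flag**, 1 − 0.95^K: K = 5, 23%; K = 9, 37%; K = 10, 40%; K = 12, 46%; K = 15, 54%.

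**Cost of one flag.** With 26 infants, p = 0.05 corresponds to a correlation with arm of r = 2.064/√(24 + 2.064²) = 0.388, so r² = 0.151. The variance of the treatment effect is multiplied by 1/(1 − 0.151) = 1.18, and 13 per arm is worth about 13/1.18 = 11. Starting from the 81% above, one noise covariate at this threshold cuts power to about 75%, and two cut it to about 66%.

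**Simulation** (10,000 trials per row, candidates unrelated to outcome). The fixed model is arm plus the 3-month value; the selected model adds every flagged candidate.

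| Candidates | Variance explained by 3-month value (assumed) | Power, fixed | Power, selected | Average loss | Fixed → selected in flagged trials |
|---|---|---|---|---|---|
| 9 | 0% | 79.4% | 75.2% | 4.2 | 78.8% → 67.6% |
| 9 | 20% | 87.4% | 83.6% | 3.8 | 87.7% → 77.6% |
| 12 | 0% | 79.8% | 74.5% | 5.3 | 79.6% → 68.0% |
| 12 | 20% | 87.2% | 81.9% | 5.3 | 87.2% → 75.9% |

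With 20% explained and 5, 10 or 15 candidates, power falls from 87% to about 85%, 82% and 80%, a loss of about 2, 5 and 7 points.

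**Movement of the estimate.** When a flag occurs, the estimate moves by roughly 0.2 to 0.3 D on average. Across the simulations this was 0.22 to 0.32 D, and 0.22/1.75 = 13% to 0.32/1.75 = 18% of the target difference.

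**If two candidates really are prognostic** (assumed to explain a further 30% jointly, with 9 or 12 candidates), naming them in advance gives about 96% power, against about 84% under selection. In flagged trials the loss against the baseline-only ANCOVA is then 7 to 8 points.

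**Type I error.** With no treatment effect, the selected model rejected in 3.7% to 5.3% of trials.

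**The case against.** The strongest reply is that this touches less of the plan than a quick reading suggests. Several stronger readings are tempting, and the documents do not support them.

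- **That the primary estimate is at risk.** The analysis named first is an unadjusted t-test, which covariate selection cannot alter, and the ANCOVA is not called primary. The point is limited to the adjusted estimate. It still matters, because the plan does not say which comparison governs if they disagree.
- **That all covariates are chosen by testing.** The 3-month value is fixed in both ANCOVAs. Only the additional covariates are open.
- **That post-randomisation variables will be adjusted for.** Illness, medication, nutrition and compliance are collected during follow-up (D.c.x), and adjusting for variables affected by treatment could bias the effect. But no text proposes them as covariates. The remark about randomisation points to baseline imbalance, and spectacle compliance has no meaning in controls, who receive no correction. At most, a restriction to baseline variables is unstated.
- **That false positives rise.** The simulations show no inflation.

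The size is also open to challenge. The plan speaks of imbalances in confounders, not in every survey item, so the tested list may be short. Correlated candidates lower the flag rate: with an assumed common correlation of 0.3 to 0.5 it is 29% to 35% for 10 candidates, not 40%, and 37% to 46% for 15, not 54%. Binary items tested by Fisher's exact test would be flagged less than 5% of the time. If the 3-month value is prognostic, even the selected ANCOVA stays close to the t-test's 81% power.

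All of this stands as a limit on the magnitude. It does not rescue the rule, which does worse than a fixed ANCOVA in every setting examined with a true effect.

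**Conclusion.** The concern holds for the additional covariates and the adjusted estimate. The plan states a selection rule, and following it with about 26 infants adds variables because they correlate with arm. Under the assumptions listed, the average cost is modest, about 2 to 7 points of power, and it is about 8 to 14 points when something is flagged. The harm is lost precision and analyst discretion, not bias or false positives. Confidence is high that the rule is there and that it is inferior to a fixed model. It is lower for the size, which depends on a candidate number, threshold, independence and prognostic strength that the plan does not give.

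**What to change.** In both ANCOVA paragraphs of section F:

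1. Delete the sentence on testing for imbalance and the open-ended reference to other identified confounders.
2. Fix the model as treatment arm plus the 3-month value of the outcome concerned.
3. If more adjustment is wanted, name at most one or two baseline covariates now, chosen because they are expected to predict refractive change.
4. State that covariates are baseline variables only.
5. Describe baseline characteristics by arm without p-values, and label any other adjusted model as a sensitivity analysis.

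The cost is wording only; no new data or infants are needed. The downside is that a chance imbalance in an unlisted variable is addressed only in a sensitivity analysis. The change does not settle whether the t-test or the ANCOVA, at 9 or 18 months, is the primary analysis. That should be stated in the same edit.
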